 - a. Lansky score \geq 40 ([Appendix 1](#)) or
 - b. Karnofsky score $>$ 50 ([Appendix 2](#)) or
 - c. Eastern Cooperative Oncology Group (ECOG) score \leq 2 ([Appendix 3](#))
8. Have adequate bone marrow reserves and liver and kidney function, as assessed by the following laboratory requirements:
 - a. Hemoglobin \geq 8 g/L
 - b. Absolute lymphocyte count \geq 500/mm³
 - c. Absolute neutrophil count \geq 1000/mm³
 - d. Platelets \geq 100,000/mm³ (untransfused [$>$ 5 days] without growth factors)
 - e. Serum creatinine \leq 1.5 x upper limit of normal (ULN) for age
 - f. Aspartate transaminase (AST) and alanine transaminase (ALT) \leq 2.5 x ULN for age
 - g. Total bilirubin $<$ 1.5 x ULN for age
 - h. International normalized ratio (INR) and activated thromboplastin time within normal institutional limits
9. Male and female subjects of childbearing potential must agree to use a highly reliable method of birth control (expected failure rate $<$ 1% per year) from the Screening visit through 28 days after the last dose of study drug. Women of childbearing potential must have a negative pregnancy test at screening.

Exclusion Criteria:

1. Radiotherapy treatment prior to the first veledimex dose:
 - a. Focal radiation \leq 4 weeks
 - b. Whole-brain radiation \leq 6 weeks
 - c. Cranio-spinal radiation \leq 12 weeks
- Note:** Subjects in Arm 2 (*i.e.*, with DIPG) must be \geq 2 weeks and \leq 10 weeks post standard focal radiotherapy (dose of 5400 to 5960 cGy and maximum dexamethasone of 1 mg/m²/day) per Inclusion Criterion 3 above.
2. Subjects with clinically significant increased intracranial pressure (*e.g.*, impending herniation or requirement for immediate palliative treatment) or uncontrolled seizures
3. Subjects whose body surface area (BSA) would expose them to $<$ 75% or $>$ 125% of the target dose per the provided dosing table
4. Known immunosuppressive disease, autoimmune condition, and/or chronic viral infection (*e.g.*, human immunodeficiency virus [HIV], hepatitis)
5. Use of systemic antibacterial, antifungal, or antiviral medications for the treatment of acute clinically significant infection within 2 weeks of first veledimex dose. Concomitant therapy for chronic infections is not allowed. Subjects must be afebrile prior to Ad-RTS-hIL-12 injection; only prophylactic antibiotic use is allowed perioperatively.

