8. Have age-appropriate functional performance:
 - a. Lansky score ≥ 40 ([Appendix 1](#)) or
 - b. Karnofsky score > 50 ([Appendix 2](#)) or
 - c. Eastern Cooperative Oncology Group (ECOG) score ≤ 2 ([Appendix 3](#))

8. Have adequate bone marrow reserves and liver and kidney function, as assessed by the following laboratory requirements:
 - a. Hemoglobin ≥ 8 g/L
 - b. Absolute lymphocyte count $\geq 500/\text{mm}^3$
 - c. Absolute neutrophil count $\geq 1000/\text{mm}^3$
 - d. Platelets $\geq 100,000/\text{mm}^3$ (untransfused [> 5 days] without growth factors)
 - e. Serum creatinine $\leq 1.5 \times$ upper limit of normal (ULN) for age
 - f. Aspartate transaminase (AST) and alanine transaminase (ALT) $\leq 2.5 \times$ ULN for age
 - g. Total bilirubin $< 1.5 \times$ ULN for age
 - h. International normalized ratio (INR) and activated thromboplastin time within normal institutional limits
9. Male and female subjects of childbearing potential must agree to use a highly reliable method of birth control (expected failure rate $< 1\%$ per year) from the Screening Visit through 28 days after the last dose of study drug. Women of childbearing potential must have a negative pregnancy test at screening.

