8.2. Exclusion Criteria

1. Radiotherapy treatment prior to the first veledimex dose:
 - a. Focal radiation ≤ 4 weeks
 - b. Whole-brain radiation ≤ 6 weeks
 - c. Cranio-spinal radiation ≤ 12 weeks
- Note:** Subjects in Arm 2 (*i.e.*, with DIPG) must be ≥ 2 weeks and ≤ 10 weeks post standard focal radiotherapy (dose of 5400 to 5960 cGy and maximum dexamethasone of 1 mg/m²/day) per Inclusion Criterion 3 above.
2. Subjects with clinically significant increased intracranial pressure (*e.g.*, impending herniation or requirement for immediate palliative treatment) or uncontrolled seizures
3. Subjects whose body surface area (BSA) would expose them to $< 75\%$ or $> 125\%$ of the target dose per the provided dosing table
4. Known immunosuppressive disease, autoimmune condition, and/or chronic viral infection (*e.g.*, human immunodeficiency virus [HIV], hepatitis)
5. Use of systemic antibacterial, antifungal, or antiviral medications for the treatment of acute clinically significant infection within 2 weeks of first veledimex dose. Concomitant therapy for chronic infections is not allowed. Subjects must be afebrile prior to Ad-RTS-hIL-12 injection; only prophylactic antibiotic use is allowed perioperatively.
6. Use of enzyme-inducing antiepileptic drugs (EIAEDs) within 7 days prior to the first dose of study drug. See [Appendix 4](#) for prohibited and permitted antiepileptic drugs.
7. Other concurrent clinically active malignant disease, requiring treatment
8. Nursing or pregnant females
9. Prior exposure to veledimex

10. Use of medications that induce, inhibit, or are substrates of CYP450 3A4 within 7 days prior to veledimex dosing without consultation with the Medical Monitor
11. Use of heparin or acetylsalicylic acid (ASA) without consultation with the Medical Monitor
 - a. The use of systemic heparinization, or any ASA containing medications, is prohibited during active dosing with veledimex. Prophylactic s.c. heparin, per institutional protocol, or heparin used for maintaining patency of an access port of PICC line is permitted.
12. Presence of any contraindication for a neurosurgical procedure
13. Unstable or clinically significant concurrent medical condition that would, in the opinion of the Investigator in conjunction with the Medical Monitor, jeopardize the safety of a subject and/or their compliance with the protocol

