16.2. Sample Size and Power Calculations

- The sample size chosen was based on clinical considerations.

- For Cohorts 1 and 3, treated at 10 mg, the 3+3 rule-based dose escalation criteria will be applied to provide an independent algorithmic safety assessment to either dose escalate from 10 to 20 mg or to consider de-escalation, as applicable. The SRC will incorporate the findings in combination with other clinical factors to make the final recommendation pertaining to dose escalation from 10 mg to 20 mg or de-escalation from 10 mg to 5 mg.
- For Cohort 4, treated at 20 mg, the 3+3 rule-based dose escalation criteria will be applied to provide an independent algorithmic safety assessment to either confirm that 20 mg dosing is safe or to potentially de-escalate to a 15 mg dose for further evaluation based on the SRC recommendation.

After the dose escalation/de-escalation portion of the study Phase II dose will be determined for both pediatric disease populations:

- recurrent or refractory supratentorial brain tumor pediatric population
- DIPG pediatric population

At the discretion of the SRC, up to 30 evaluable DIPG subjects may be enrolled in the Phase II expansion cohort, which will support time to OS estimation. The projection of this sample size is based on clinical considerations as well as numbers to obtain sufficient preliminary assessments of overall response. Additional details will be provided in the Statistical Analysis Plan.

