## **8. PROTOCOL DEVIATIONS**

A protocol deviation is any change, divergence, or departure from the study design or procedures defined in the protocol.

- Important protocol deviations are a subset of protocol deviations that may significantly impact the completeness, accuracy, and/or reliability of the study data or that may significantly affect a subject's rights, safety, or well-being.
- Where applicable, important protocol deviations will be categorized as major protocol deviations.
  - Protocol deviations that are not deemed important protocol deviations are classified as minor protocol deviations
- The list of protocol deviations along with whether the deviation is classified as major or minor will be finalized prior to database lock.

No subject will be removed from any analysis population because of a protocol deviation.

In accordance with ICH E3, subject eligibility violations and important post- treatment protocol deviations will be identified and listed by subject ID and study center. Major deviations that are considered to potentially impact the efficacy or safety analyses will be tabulated. Important protocol deviations will be identified prior to database lock. Protocol deviations will be listed and summarized by type.

- Deviation from inclusion/exclusion criteria
- Withdrawal criteria met during the study but subject ID was not withdrawn
- Prohibited concomitant medications
- Treatment deviation
- Other protocol deviation

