### 13.4. Clinical Laboratory Assessments

Clinical laboratory assessments include hematology, coagulation, serum chemistry and urinalysis. Laboratory tests will be performed in a central laboratory. Laboratory values will be converted to standardized units. Only numerical values will be used for summary of continuous parameters.

For hematology, coagulation and serum chemistry laboratory parameters, subject listings will be provided for values at baseline and changes from baseline instead of descriptive summary tables by treatment arm, dose cohort and visit for the OSP.

In addition, laboratory test results will be categorized by CTCAE toxicity grades according to the normal ranges of the central laboratory. Subject listings will provide the shift from baseline to worst post-baseline extreme values denoting the visit for which the worst post-baseline shift occurred. Laboratory results with toxicity grades missing at either baseline or at post-baseline will not be used for summarizing the worst post-baseline shift by subject ID. The number of subjects who have both baseline and post-baseline laboratory values will be summarized where applicable.

Urinalysis laboratory parameters are summarized by subject ID (instead of Frequency tables used to summarize the urinalysis laboratory parameters by treatment arm and dose cohort, and visit.).

Separate listings by subject ID for each subject ID visit will be summarized for all laboratory tests where applicable for the OSP. Both laboratory parameters' values in the original unit collected and standardized units will be listed.

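### The hemoglobin inclusion criterion, written as 8 g/L in Protocol Section 8.1 and the synopsis, sets no effective numeric floor; its value and unit need confirming.

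*Protocol*

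**What the plan says.** Section 8.1 of the Protocol lists a set of laboratory requirements under the lead-in "Have adequate bone marrow reserves and liver and kidney function, as assessed by the following laboratory requirements". The first of them is "Hemoglobin ≥ 8 g/L". The Inclusion Criteria in the Clinical Protocol Summary (Section 4) carry the same line with the same unit.

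The other blood-count lines in the list are an absolute lymphocyte count of at least 500/mm³, an absolute neutrophil count of at least 1000/mm³ and platelets of at least 100,000/mm³.

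Neither the Protocol nor the SAP gives any other hemoglobin threshold, and neither states hemoglobin in a different unit. SAP Section 8 includes "Deviation from inclusion/exclusion criteria" among the types of deviation to be listed and summarized. SAP Section 13.4 says "Laboratory values will be converted to standardized units" but names no unit for hemoglobin.

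**The concern.** An eligibility floor is useful only if some plausible candidate can fail it. The lead-in says this one helps to establish marrow reserve. That is a real screening question here: subjects may have had earlier cytotoxic or nitrosourea treatment (Section 8.1 sets washout periods for both), and they go on to intracranial surgery and injection. At 8 g/L the floor appears to lie below any value that a surgical candidate could have.

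Two things would follow. The written protocol would offer no numeric protection on hemoglobin. And the record of eligibility deviations would be silent on hemoglobin whatever values were enrolled, because nobody could breach the criterion as worded.

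**Working it through.** **Inputs.** The floor is 8 g/L (Protocol Section 8.1 and synopsis). The conversion is 1 g/dL = 10 g/L. The floor is a stated threshold and not a derived figure, so the plan has no calculation to reproduce.

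**Step 1, conversion.** 8 g/L ÷ 10 = 0.8 g/dL.

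**Step 2, what that level means.** Hematocrit is approximately hemoglobin divided by mean cell hemoglobin concentration. The documents do not give that concentration, so I assume 30 to 36 g/dL:
- at 36 g/dL: 0.8 / 36 = 2.2%
- at 30 g/dL: 0.8 / 30 = 2.7%

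A child able to undergo craniotomy or stereotactic surgery would not have a hematocrit of 2% to 3%.

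**Step 3, can the line exclude anyone?** Take a hemoglobin of 4 g/dL, purely as an illustration of severe anemia. It equals 40 g/L, and 40 / 8 = 5, so it passes at five times the written floor. The lymphocyte, neutrophil and platelet lines can each exclude a plausible candidate; the hemoglobin line cannot.

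**Step 4, deviation check.** Suppose hemoglobin is held in g/L after the conversion in SAP Section 13.4. The literal rule for an eligibility deviation is then hemoglobin < 8. By Steps 2 and 3 that flags no subject, so the inclusion/exclusion category in SAP Section 8 would contain no hemoglobin entries.

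**Step 5, is it a reading artifact?** The same numeral and unit stand in Section 8.1, in the synopsis and in the Amendment 1 change table. The change table is superseded material and is used here only to show that three separate places agree. A text-extraction error in all three is unlikely.

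**Step 6, who is still affected.** SAP Section 2.1.1 reports Arm 1 concluded after three subjects, with its database locked on 08-Nov-2019. SAP Table 2 shows Cohort 3 enrolling and Cohort 4 still to come. Against the planned total of about 45, at most 45 − 3 = 42 subjects would enter under this criterion in Arm 2, including any already enrolled in Cohort 3.

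**The case against.** The strongest reply is that the hemoglobin line is only one gate.
- Section 8.2 excludes "Presence of any contraindication for a neurosurgical procedure" (exclusion 12). Exclusion 13 bars a concurrent condition that, in the Investigator's opinion with the Medical Monitor, would endanger the subject.
- The registration footnote to Protocol Table 1 requires both of them to accept eligibility before the first dose of study drug.
- Section 12.3.4 repeats the hematology panel and confirms eligibility at Day 0, with the panel allowed on Day -1 instead.

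This stands. A reader might infer that the plan as written admits severely anemic children. The documents do not support that: other provisions could stop such a child, although by judgment and without a hemoglobin value. What fails is this one line, not the whole eligibility process.

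Three other strong readings also go too far.
- **That the criterion excludes 0% of candidates, as a measured result.** No hemoglobin distribution is given, so this is a physiological inference.
- **That sites will apply different units and code deviations differently.** Nothing shows this. About 3 to 5 centers are planned, registration is centralized and the Medical Monitor takes part in each eligibility decision. All of these limit divergence.
- **That the intended unit is known.** Read in g/dL, the same numeral would be 80 g/L, ten times the written floor. Sites may well assume some such correction, but neither document states the intent.

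It is also fair to say that the analysis is untouched. No endpoint, DLT rule or estimate uses this threshold. On sample size, Section 16.2 says "The sample size chosen was based on clinical considerations". SAP Section 8 removes nobody from an analysis population for a deviation. SAP Section 5.3 does restrict the ESP for major deviations that confound the key efficacy endpoints, but nothing suggests that a hemoglobin value would do so.

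None of this makes the line work. The judgment-based safeguards limit the harm; they do not supply the numeric floor that the criterion purports to set.

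**Conclusion.** The point holds in a limited form. The hemoglobin criterion is operative text, appears identically in two current places, is corrected nowhere, and cannot serve the purpose given in its own lead-in. Its literal value is 0.8 g/dL, so it adds no effective numeric hemoglobin floor, and a literal deviation check would find nothing.

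The conversion is exact. The step from 0.8 g/dL to no effective floor rests on general physiology and on the assumed cell hemoglobin concentration in the working. The conclusion is not sensitive to that range, since both ends give a hematocrit below 3%.

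The practical reach is confined to Arm 2 screening and the eligibility-deviation listing. It is worth correcting while Arm 2 is enrolling, but it does not threaten the trial's estimates.

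**What to change.** Ask the sponsor to confirm the intended hemoglobin value and unit, then correct Section 8.1 and the synopsis in the same change so that they continue to agree. The change should name the hemoglobin line under the laboratory requirements. Section 8.1 numbers both the performance-status criterion and the laboratory criterion as 8, so a reference to item 8a alone could be taken as the Lansky score. The numbering can be repaired at the same time.

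Once the unit is confirmed, the SAP or its programming specification should state the hemoglobin unit used for any eligibility check, and subjects already enrolled in Arm 2 should be checked against the confirmed criterion.

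The cost is one line in two places plus a short data check. An amendment or an administrative memo would serve; the Amendment 2 change table shows that this protocol has used memos before. The choice of threshold is left to the sponsor.

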8.2. Exclusion Criteria

1. Radiotherapy treatment prior to the first veledimex dose:
 - a. Focal radiation ≤ 4 weeks
 - b. Whole-brain radiation ≤ 6 weeks
 - c. Cranio-spinal radiation ≤ 12 weeks
- Note:** Subjects in Arm 2 (*i.e.*, with DIPG) must be ≥ 2 weeks and ≤ 10 weeks post standard focal radiotherapy (dose of 5400 to 5960 cGy and maximum dexamethasone of 1 mg/m²/day) per Inclusion Criterion 3 above.
2. Subjects with clinically significant increased intracranial pressure (*e.g.*, impending herniation or requirement for immediate palliative treatment) or uncontrolled seizures
3. Subjects whose body surface area (BSA) would expose them to $< 75\%$ or $> 125\%$ of the target dose per the provided dosing table
4. Known immunosuppressive disease, autoimmune condition, and/or chronic viral infection (*e.g.*, human immunodeficiency virus [HIV], hepatitis)
5. Use of systemic antibacterial, antifungal, or antiviral medications for the treatment of acute clinically significant infection within 2 weeks of first veledimex dose. Concomitant therapy for chronic infections is not allowed. Subjects must be afebrile prior to Ad-RTS-hIL-12 injection; only prophylactic antibiotic use is allowed perioperatively.
6. Use of enzyme-inducing antiepileptic drugs (EIAEDs) within 7 days prior to the first dose of study drug. See [Appendix 4](#) for prohibited and permitted antiepileptic drugs.
7. Other concurrent clinically active malignant disease, requiring treatment
8. Nursing or pregnant females
9. Prior exposure to veledimex

10. Use of medications that induce, inhibit, or are substrates of CYP450 3A4 within 7 days prior to veledimex dosing without consultation with the Medical Monitor
11. Use of heparin or acetylsalicylic acid (ASA) without consultation with the Medical Monitor
 - a. The use of systemic heparinization, or any ASA containing medications, is prohibited during active dosing with veledimex. Prophylactic s.c. heparin, per institutional protocol, or heparin used for maintaining patency of an access port of PICC line is permitted.
12. Presence of any contraindication for a neurosurgical procedure
13. Unstable or clinically significant concurrent medical condition that would, in the opinion of the Investigator in conjunction with the Medical Monitor, jeopardize the safety of a subject and/or their compliance with the protocol

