The starting dose in Cohort 1 will be 10 mg, which is approximately 5.3 mg/m^2 . The actual administered dose will depend on the subject's BSA and available capsule sizes ([Table 4b](#)). Because veledimex is an PO agent and is supplied in a fixed capsule size (5 mg and 20 mg), the actual administered dose is based on a subject's BSA and is bound by the rounding constraints set by 5 mg. The Sponsor developed a BSA-adjusted dosing algorithm designed to enable dosing within 25% of the target dose in mg/m^2 .

If a subject's BSA would expose the subject to $< 75\%$ or $> 125\%$ of the target assigned dose, the actual administered dose will be modified to ensure that the target dose in mg/m^2 is achieved. Minimum BSA restrictions for enrollment must be met in order for a subject to be appropriately dosed. Potential subjects whose BSAs do not have a correlated administered dose may be enrolled at the discretion of the Investigator and the Medical Monitor but will not be considered in the assessment of the recommended Phase II pediatric dose. Dosing of these subjects can only commence once the cohort has been reviewed by the SRC and determined that the dosing at the specified level (10 mg or 20 mg) is appropriate for escalation or as the recommended Phase II pediatric dose. These subjects will be analyzed separately.

The dosing table ([Table 4b](#)) illustrates this algorithm and captures the BSA adjusted-actual administered dose that subjects would receive at assigned dose levels based on a minimum capsule size of 5 mg.

Table 4b: Veledimex Dosing Table

Cohort	Target Dose (mg)	Min BSA (m ²)	Min BSA Target Dose (mg)	Percentage of Expected Dose (%)	Max BSA (m ²)	Max BSA Target Dose (mg)	Percentage of Expected Dose (%)	Actual Dose ^a (mg)
10 mg	5.3	0.5	10	189	0.75	6.7	126	5 ^b
10 mg	5.3	0.76	6.6	124	1.26	4.0	75	5
10 mg	5.3	1.27	3.9	74	1.5	3.3	63	5
10 mg	5.3	1.27	7.9	149%	1.5	6.7	126%	10 mg ^b
10 mg	5.3	1.51	6.6	125%	2.53	4.0	75%	10 mg
Cohort	Target Dose (mg)	Min BSA (m ²)	Min BSA Target Dose (mg)	Percentage of Expected Dose (%)	Max BSA (m ²)	Max BSA Target Dose (mg)	Percentage of Expected Dose (%)	Actual Dose ^a (mg)
20 mg	10.6	0.5	10	94%	0.63	7.9	75%	5 mg
20 mg	10.6	0.64	7.8	74%	0.75	6.7	63%	5 mg
20 mg	10.6	0.64	15.6	147%	0.75	13.3	126%	10 mg ^b
20 mg	10.6	0.76	13.2	124%	1.25	8.0	75%	10 mg
20 mg	10.6	1.26	11.9	112%	1.87	8.0	75%	15 mg
20 mg	10.6	1.88	10.6	100%	2.53	7.9	75%	20 mg

^a The actual dose is \pm 25% of the target dose.

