^b Subjects in this BSA range may be dosed at the discretion of the Investigator and the Medical Monitor

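### Exclusion 3 bars out-of-range BSA without exception, yet Section 7.1 and Table 4b let some of these children be dosed, and two BSA bands carry two doses a factor of two apart

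*Protocol*

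**What the plan says.** **Eligibility.** Protocol 8.2, exclusion 3 (repeated in the synopsis) excludes "Subjects whose body surface area (BSA) would expose them to" less than 75% or more than 125% of the target dose in the dosing table. No waiver is written. Exclusions 10 and 11 in the same list do contain a Medical Monitor consultation clause.

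**Dosing text.** Protocol 7.1 (repeated in the synopsis) describes an algorithm "designed to enable dosing within 25% of the target dose", with the dose "bound by the rounding constraints set by 5 mg". For a subject below 75% or above 125% of the target assigned dose, it says "the actual administered dose will be modified to ensure that the target dose" is achieved. The same paragraph adds: "Potential subjects whose BSAs do not have a correlated administered dose may be enrolled at the discretion of the Investigator and the Medical Monitor". Those subjects are dosed only after the Safety Review Committee (SRC) has reviewed the cohort, are left out of the recommended-dose assessment, and are analysed separately.

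**Dosing table.** Table 4b and its synopsis copy list BSA 1.27-1.5 m² twice in the 10 mg cohort and BSA 0.64-0.75 m² twice in the 20 mg cohort, each time at 5 mg and at 10 mg. The 5 mg row of the first pair reads "1.27 3.9 74 1.5 3.3 63 5". Footnote a puts the actual dose within 25% of target. Footnote b says "Subjects in this BSA range may be dosed at the discretion of the Investigator and the Medical Monitor". It is attached to the 10 mg row of each pair and to the 5 mg row for BSA 0.5-0.75 m² in the 10 mg cohort. The two 63-74% rows do not carry it.

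**Analysis sets.** The ESP in Protocol 4, 14 and 16.1 requires subjects to be BSA conformant, a term left undefined. SAP 5.3 defines the ESP without that condition and uses it for escalation and for DLT evaluation.

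**The concern.** A child in one of these BSA bands meets an exclusion criterion that has no exception, yet appears in the dosing table with one or two listed doses, some of them expressly open to discretion. A site cannot tell from the protocol whether the child may be enrolled or, in two bands, which of two doses applies.

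Two things are at stake. The first is patient safety: the table allows a twofold difference in dose for the same child. The second is classification. A child dosed under footnote b is permitted by the table and is at the same time an inclusion/exclusion deviation under SAP Section 8. Whether that child counts in the set used for DLTs then depends on which document's ESP definition is applied.

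**Working it through.** **Inputs.** The targets are 5.3 mg/m² (10 mg cohort) and 10.6 mg/m² (20 mg cohort). BSA limits and doses come from Table 4b, and the dose step is 5 mg.

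**Step 1: reproduce the table.** Percent of target = 100 × (dose / BSA) / target. Both ends of all 11 rows (22 percentages) reproduce to within 1 percentage point. The rows outside 75-125% are:

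| Cohort | BSA (m²) | Dose | Lower BSA limit | Upper BSA limit | Footnote b |
|---|---|---|---|---|---|
| 10 mg | 0.5-0.75 | 5 mg | 5/0.5/5.3 = 188.7% | 5/0.75/5.3 = 125.8% | yes |
| 10 mg | 1.27-1.5 | 5 mg | 5/1.27/5.3 = 74.3% | 5/1.5/5.3 = 62.9% | no |
| 10 mg | 1.27-1.5 | 10 mg | 10/1.27/5.3 = 148.6% | 10/1.5/5.3 = 125.8% | yes |
| 20 mg | 0.64-0.75 | 5 mg | 5/0.64/10.6 = 73.7% | 5/0.75/10.6 = 62.9% | no |
| 20 mg | 0.64-0.75 | 10 mg | 10/0.64/10.6 = 147.4% | 10/0.75/10.6 = 125.8% | yes |

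These five of 11 rows contradict footnote a and meet exclusion 3. Elsewhere, the upper BSA limits 1.26, 0.63 and 2.53 m² compute to 74.9%, 74.9% and 74.6% and are printed as 75%. That is rounding and is not counted here.

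**Step 2: size of the dose conflict.** In each paired band the listed doses differ by 10/5 = 2, and both lie outside 75-125%.

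**Step 3: can a 5 mg step reach the limits?** A dose is within range for BSA from dose/(1.25 × target) to dose/(0.75 × target).

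- Target 5.3: 5 mg covers 0.755-1.258 m² and 10 mg covers 1.509-2.516 m². Nothing covers BSA below 0.755 m² or between 1.258 and 1.509 m².
- Target 10.6: 5 mg covers 0.377-0.629 m² and 10 mg covers 0.755-1.258 m². Nothing covers 0.629-0.755 m².
- The next multiple is no help. In the paired bands 15 mg gives at least 188.7%. For BSA 0.5-0.75 m² in the 10 mg cohort, 10 mg gives at least 251.6%.

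If the sentence on modifying the dose is meant to apply in these bands, it cannot be carried out.

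**Step 4: route to the DLT set.** Protocol 16.1 lists receipt of the cohort-specific veledimex dose and BSA conformance as separate conditions. SAP 5.3 keeps the first and omits the second, and the changes listed in SAP 6.1 do not mention the omission. SAP 5.3 also removes subjects with certain major deviations, but SAP Section 8 says that no deviation removes a subject from any population, so that clause does not reliably close the gap.

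As an illustration, the recommended dose turns on whether at least 33% of a cohort have DLTs. Two of six is 33.3% and meets the criterion. With one further subject without a DLT, two of seven is 28.6% and does not.

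**The case against.** Four points can be made in the plan's defence.

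- **The dose-modification sentence may not be a separate rule.** It refers to the assigned dose, which is how Table 4a labels the cohort doses of 10 mg and 20 mg. It can be read as describing the BSA adjustment itself, with exclusion 3 then removing whoever is still out of range. A reader might infer three flatly contradictory rules. The text is ambiguous and does not establish that. The conflict that stands is between exclusion 3 and discretionary dosing.
- **The protocol protects the dose decision.** Discretionary subjects are held until SRC review, left out of the recommended-dose assessment and analysed separately. Footnote b in the synopsis refers back to that text. The protocol ESP also demands BSA conformance. A reader might infer that the conflict contaminates 3+3 decisions under the protocol. These safeguards speak against it. The remaining route is the SAP's ESP definition.
- **Sites do not act alone.** The Medical Monitor must agree eligibility, is contacted before each daily dose, and shares the discretion in footnote b. A reader might infer that sites would treat the same child differently. The documents support only that they could.
- **The paired rows may be illustrative.** Each pair may show that neither multiple conforms, with footnote b marking the only row open to discretion. That is plausible, but no text says so. The 63-74% rows still show an actual dose under a footnote that is untrue of them.

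The objection therefore narrows the consequences. It does not remove the conflict over eligibility, supply a rule for choosing between paired rows, or make footnote a correct.

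**Conclusion.** The point holds as an internal inconsistency that should be corrected. Exclusion 3 and the discretionary provision cannot both apply as written to the bands carrying footnote b. Two bands list doses a factor of two apart with no rule for choosing, and footnote a is untrue of five of 11 rows, including one that reaches 189% of target.

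The statistical consequence is conditional. Under the protocol, the effect on 3+3 decisions is limited by the SRC hold, the separate analysis and the ESP condition, although that condition rests on an undefined term. Under SAP 5.3 as written, such subjects could enter the DLT set. The two-of-seven example shows how one subject could matter and is not a forecast: the documents do not say how many subjects fall in these bands. SAP 13.2.2 does plan exposure categories below 75% and above 125%, so their presence is anticipated.

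The conclusion assumes that the rows and footnotes are as shown in both copies of the table, which agree.

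**What to change.** Reconcile exclusion 3, the Section 7.1 text and both copies of the dosing table (with the matching synopsis text) so that:

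- one rule covers out-of-range BSA and, if an exception is intended, exclusion 3 refers to it;
- the sentence on modifying the dose states which step of the algorithm it describes;
- each BSA band has one unambiguous entry;
- footnote a is true of every row it covers.

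Define BSA conformant once in the protocol and carry the condition into SAP 5.3, so that both documents use the same ESP for escalation and DLT evaluation. Which eligibility rule or dose applies is the sponsor's decision. The cost is a wording and table edit in the protocol and one added condition in the SAP, with no new data collection.
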